We recognize that there are some potential patient risks related to the study. We will work closely with the Institutional Review Board at the University of Utah to ensure that procedures are in place to protect the rights and welfare of patients and parents. Use of the Self-Management for Children with Medical Complexity (MyChild^{CMC}) application will not interfere with or change health care provider usual care of the patient's conditions other than by increasing parent engagement in the care of their child's complex chronic conditions and by providing additional objective data for health care providers to augment their ability to make informed medical decisions for timely treatments. No adverse events that would harm study participants are anticipated. Participation in ongoing assessments of crosscutting symptoms and caregiver burden is voluntary and individuals can discontinue participation at any time. The principal risks to participants of this research are loss of privacy and confidentiality, including use of electronic databases for potential subject identification, and potential breach of confidentiality through disclosure of protected health information for parents responding to the ongoing assessment of crosscutting symptoms. Installing rigorous security protections on data management, issuing regular reminders to project staff to change their passwords often, and adherence to HIPAA and IRB privacy and data security requirements will mitigate these risks. We will monitor positive and potential adverse outcomes that may arise to participants in this study.

2. Describe the potential benefits to society AND to participants (do not include compensation):

This study will facilitate early identification of acute deteriorations of crosscutting symptoms to facilitate timely decisionmaking in order to prevent an ED or hospital admission. We are not making any claims that participants will benefit directly from participation in this study. However, based on our preliminary studies with the electronic-AsthmaTracker showing significant reduction in ED/hospital admissions, it is likely that patient in the current study will have improved outcomes, including improved QOL and reduced ED/hospital admissions. In addition, we anticipate that parents will have improved satisfaction, self-management skills, QOL, and reduced impact of caregiving. Further, the health care provider will benefit from additional objective data to facilitate timely decision-making. Our project will provide useful information about factors critical to caregiver self-management engagement and burnout that can be addressed to facilitate broad dissemination of self-management systems or versions of them, may be adopted by clinics and health care organizations nationwide to improve care of CMC overall.

3. Are there any costs to the participants from participation in research?

🔿 Yes 🌑 No

If yes, specify:

4. Is there any compensation to the participants?

• Yes 🔿 No

a. If yes, answer the following:

Specify overall amount:

Participants in the focus group and usability testing will receive \$50 gift card for participating.

Participants enrolled to use the MyChildCMC app will be compensated in total \$120 in gift cards: \$40 for completing enrollment and baseline surveys \$40 each for 2 follow-up surveys that will be sent via RedCAP.

All participants enrolled to use the MyChildCMC app will receive a new pulse oximeter (valued at \$20) to measure their child's blood oxygen level as part of the study.

Participants randomized to MyChildCMC group will receive a stethoscope (valued at \$5) to measure their child's respiratory rate as part of the study.

b. Specify when participants will be paid (e.g. at each visit, at end of study, etc.): Participants in focus group and usability testing will receive \$50 gift card at then end of the session.

Participants enrolled to use the MyChildCMC app will receive \$40 gift card and a new pulse oximeter and a stethoscope at end of enrollment and completing baseline surveys. Thereafter, they will receive \$40 gift card as they complete two follow-up surveys that will be sent via RedCAP. The gift cards will be sent by email once confirming that the follow-up surveys have been completed.

- c. If applicable, please specify payment by visit or other time interval (e.g. \$10 per visit, etc.): \$40 at enrollment, pulse oximeter at enrollment, \$40 for first follow-up survey completion, \$40 for second follow-up survey completion.
- d. If applicable, explain plan for prorating payments if participant does not complete the study: Not applicable.

7/9/2021

IRB 00088596

RB_00088596		
	Created: 12/9/2015 12:01 PM	IRB_00088596 7. HIPAA & the Covered Entity
ו: [name] MD, MS, חPH	Submitted: 2/12/2016	
HILDREN WITH CHRONIC	MEDICAL COMPLEXITY	
	7. HIPAA and	d the Covered Entity
1. Does this study i information? ● Yes ○ No	nvolve Protected Health I	nformation (PHI) or de-identified health
a. Select the m	ethod(s) of authorization	that will be used:
(Consent and) A	Authorization Document	
Waiver or Altera	tion of Authorization	
b. Will PHI be d O Yes 🌑 No	lisclosed outside the Cov	ered Entity?
Does this study i	nvolve any of the followir	
2. The investigation ○ Yes ● No	al use of a drug?	ıg:
Yes No	nal use of a drug? nal use of a medical devic	
 Yes No 3. The investigation Yes No 	nal use of a medical devic	
 Yes No 3. The investigation Yes No 4. Is this an investig Yes No 	nal use of a medical devic	e? vice trial lead by the Principal Investigator?
 Yes No 3. The investigation Yes No 4. Is this an investig Yes No 5. Exposure to radio Yes No 	nal use of a medical devic	e? vice trial lead by the Principal Investigator? iation?
 Yes No 3. The investigation Yes No 4. Is this an investig Yes No 5. Exposure to radia Yes No 6. A Humanitarian E Yes No 	nal use of a medical devic gator-initiated drug or dev oisotopes or ionizing rad	e? vice trial lead by the Principal Investigator? iation?
 Yes No 3. The investigation Yes No 4. Is this an investig Yes No 5. Exposure to radio Yes No 6. A Humanitarian E Yes No 7. Genetic testing a Yes No 	nal use of a medical devic gator-initiated drug or dev oisotopes or ionizing rad Device Exemption (HDE)? nd/or analysis of genetic	e? vice trial lead by the Principal Investigator? iation?
 Yes No 3. The investigation Yes No 4. Is this an investig Yes No 5. Exposure to radio Yes No 6. A Humanitarian E Yes No 7. Genetic testing a Yes No 8. Creating or sendio uses? 	nal use of a medical devic gator-initiated drug or dev oisotopes or ionizing rad Device Exemption (HDE)? nd/or analysis of genetic	e? vice trial lead by the Principal Investigator? iation? data?

 Introducing Recombinant or Synthetic Nucleic Acids (e.g. viral vectors, oligonucleotides) or cells containing recombinant nucleic acids (e.g. CAR-T) into participants; OR

	 Introducing other biological materials (e.g. bacteria, viruses) into participants. Yes No
10.	Does this study involve any of the following? ■ Cancer Patients
	 Cancer Hypothesis
	 Cancer risk reduction
	 Cancer prevention Yes No
11.	Any component of the Center for Clinical and Translational Science (CCTS)? O Yes No The Clinical Services Core (CSC)? O Yes No

7/9/2021		IRB_00088596
IRB_00088596	Created: 12/9/2015 12:01 PM	IRB_00088596 - Request for Waiver of Authorization
PI: [name]	Submitted: 2/12/2016	
Title: SELF-MANAGEME CHILDREN WITH CHRO COMPLEXITY	ENT INTERVENTION FOR INIC MEDICAL	
	Request for Wai	ver or Alteration of Authorization
Request for Waiv	er of Authorization for	Recruitment Only
		rder to identify eligible participants BEFORE approaching them to obtain consent and
authorization. All other v	vaiver requests must be entered b	elow.
Other Requests f	or Waivers of Authoriza	ation:
 Click "Add" below t 	to add a new waiver request to this	s application.
Click the waiver na	me link to edit a waiver that has a	already been created.
 To delete a waiver 	request, contact the IRB.	
Date Ty Created Ty	pe of Request Purpose	e of Waiver Request

view 1/12/2016 Waiver of Authorization Record review for recruitment and chart review for all data collection through EDW.

IRB_00088596

IRB Smart Form

IRB_00088596

Created: 12/9/2015 12:01 PM Submitted: 2/12/2016

PI: [name]

Title: SELF-MANAGEMENT INTERVENTION FOR CHILDREN WITH CHRONIC MEDICAL COMPLEXITY

	Request for Waiver or Alteration of Authorization
	-
1.	Purpose of the Waiver Request: Record review for recruitment and chart review for all data collection through EDW.
2.	Type of Request: Waiver of Authorization
3.	List the identifying information you plan to collect or keep a link to (e.g. names, dates, or identification numbers such as social security numbers or medical record numbers, etc). EMPI, Encounter, Admit Date, Discharge Date, Date of Birth, Age, Sex, Race, Weight, Height, PCP, Insurance Code, Composite Score, Length of Stay, Cost, Hospital/ED Readmissions
4.	Explain why the PHI to be used or disclosed is the minimum necessary to accomplish the research objectives: The PHI is a prerequisite to identifying and pulling charts for manual review, and for administrative database information retrieval. The PHI we are collecting will be used to improve our ability to provide high quality complex medical care and will provide critical information for quality improvement.
5.	Explain why the research could not practicably be conducted without the waiver of authorization. For example, complete the following sentence: "If I had to obtain authorization, the research could not be conducted because" The PHI accessed through chart review will provide Quality Improvement (QI) data as it will be given to pediatric clinical program leaders. Impacts of QI interventions on hospitalization outcomes and patient related measures targeted at reducing re-admissions have not been evaluated. By obtaining authorization, selection bias is introduced, which minimizes the generalizability of the study outcomes.
6.	Describe your plan to protect the identifiers from improper use and disclosure, and indicate where the PHI will be stored and who will have access: All investigators and project staff sign confidentiality pledges annually and receive IRB and HIPAA privacy and data security compliance training annually. All source/legacy data files regarding patient EDW data will be stored behind the Intermountain fire wall and will be accessed only by staff members working on this study.
7.	The identifiers must be destroyed at the earliest opportunity consistent with conduct of the research, unless there is a health or research justification for retaining the identifiers or such retention is otherwise required by law. Describe how and when you will destroy the identifiers, or justify their retention: Individual identifier information will be removed from study data files as soon as possible in the data processing steps. Unique study-specific identifiers will be assigned to support accurate linkage of data on the same individual across multiple data files. We will maintain a data dictionary linking the study identifier to the personal identifiers until 7 years after the IRB approval for the study expires (to permit re-analysis of the data files to respond reviewers comments for publication purposes).
8.	Describe the measures you will take to ensure the PHI will not

L

be reused or disclosed to any other person or entity, except as required by law, for authorized oversight of the research study, or for other research approved by the IRB:

Installing rigorous security protections on data management, and adherence to HIPAA and IRB privacy and data security requirements will help mitigate potential risks. At the completion of the study and after publication of results, all data will be destroyed.

IRB_00088596	Created: 12/9/2015 12:01 PM	IRB_00088596 8. Resources and Responsibilities
PI: [name]	Submitted: 2/12/2016	

Title: SELF-MANAGEMENT INTERVENTION FOR CHILDREN WITH CHRONIC MEDICAL COMPLEXITY

8. Resources and Responsibilities

1. * State and justify the qualifications of the study staff:

The clinical research coordinator ,[name], will be consenting and collecting data from participants. This individual is qualified by education, training, and experience to perform the delegated tasks.

2. * Describe the training that study staff and investigators will receive in order to be informed about the protocol and understand their research-related duties and functions:

The PIs [name], [name], [name], [name] and [name] as well as the clinical research coordinator, [name], will be involved in research-related activities. Meetings will occur between the PI and other members of the research team weekly regarding study procedures and research-related duties. The PI and staff have completed all required training regarding regulatory requirements including proper conduct of research.

- 3. * Describe the facilities where the research activities will be performed (e.g. hospitals, clinics, laboratories, classrooms/schools, offices, tissue banks, etc.). Inpatient floors at PCH, Outpatient Services PCH
- * Describe the medical or psychological resources available at this site (and other participating sites, if applicable) that participants might require as a consequence of the research. If not applicable, please state. Not Applicable

IRB_00088596

Created: 12/9/2015 12:01 PM

Documents and Attachments

PI: [name] Submitted: 2/12/2016

Title: SELF-MANAGEMENT INTERVENTION FOR CHILDREN WITH CHRONIC MEDICAL COMPLEXITY

_____ Documents and Attachments _

lf any	/ of your docur	nents (such as inv	estigational brochures, sponso	protocols, advertisements, etc.) are no	t available in an electronic format, please scan	
and s	and save them as PDF files or contact our office for assistance.					
	-	ts: Please use the erentiate from earli	•	content of each form. The name you er	nter will be listed on your approval letter. Use	
Cons Cons Spon	ent Document sor Protocol 0	Control Group 04 Treatment Group 4/14/05 Version 2 Highlighted Chang	4/14/05			
Apple	e/Macintosh Us	sers:MS Word doc	uments must have a .doc file e:	xtension. See ERICA home page for ins	structions.	
	Print Viev	v: IRB Draft Pı	rotocol Summary			
	eProtoco	I Summary:				
	Name	Version	Date Created	Date Modified	Date Approved	
	There are	no items to dis	splay			
	Consent I	Documents, C	onsent Cover Letters, C	onsent Information Sheets, Co	onsent Scripts, etc.:	
	Name	Version	Date Created	Date Modified	Date Approved	
	There are	no items to dis	splay			
	Parental I	Permission Do	ocuments:			
	Name	Version	Date Created	Date Modified	Date Approved	
	There are	no items to dis	splay			
	Assont D	ocuments:				
	Name	Version	Date Created	Date Modified	Date Approved	
		no items to dis	splay			
	VA Conse Name	ent Documents Version	s: Date Created	Date Modified	Date Approved	
		no items to dis		Date Moumeu	Date Approved	
	-		es, Interview Scripts, etc			
	Name	Version	Date Created	Date Modified	Date Approved	
	I nere are	no items to dis	spiay			
	Full Proto	ocol (company	r protocol, sponsor prot	ocol, investigator-initiated pro	otocol, etc.):	
	Name	Version	Date Created	Date Modified	Date Approved	
	There are	no items to dis	splay			
	Investigat	tional Brochu	re (IB) for Investigationa	Il Drug or Drug/Device Packag	e Insert:	
	Name	Version	Date Created	Date Modified	Date Approved	

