Please review these previously entered fields as you fill out the new form:
Sponsor: HRSA MATERNAL & CHILD HEALTH BUREAU Contact: [name], MPH, FAAP Senior Medical Advisor/Acting Deputy Director Division of Services for Children with Special Health Needs Maternal and Child Health Bureau [contact] office [contact] mobile [contact] Grant Number: HHSH25020170038G Awardee: University of Utah, [name] Effective Date Start: 12/19/2018
a. Are you receiving award or contract management for the sponsored funds through the University of Utah Office of Sponsored Projects?
● Yes ◯ No
If yes, select the associated OSP Proposal ID/DSS through eAward to link it to the ERICA system.
You must have a fully approved Proposal ID/DSS number through eProposal which will show up in eAward after OSP has integrated the ID. To access the eAward application, use the instructions on the OSP website.
Link to a Proposal ID/DSS through eAward

7/0/	200	21
7/9/	20	Z I

IRB_00088596

3. Participants

IRB 00088596	Created: 12/9/2015 12:01 PM

PI: [name]

Submitted: 2/12/2016

Title: SELF-MANAGEMENT INTERVENTION FOR CHILDREN WITH CHRONIC MEDICAL COMPLEXITY

		3. Participants
		-
1.	Ages of Participants:	
	Less than 7 years old	(Parental permission form needed)
	7 to 17 years old	(Parental permission and assent form needed)
	18 and older	(Consent form needed)

2. Specific age range of participants (e.g., 7-12 years old, 60+, etc.): Children age 1-20 years old with complex medical conditions and their parent caregivers

3. Indicate any vulnerable participant groups (other than children) included:

Individuals with Cognitive or Decisional Impairment

If "Other", please specify:

If "None" and no children are involved, answer the following question. Has the participant selection process overprotected potential subjects who are considered vulnerable so that they are denied opportunities to participate in research? ○ Yes ● No

4. Number of participants to be included and/or enrolled in this entire study, across all study locations: 300

At Utah prior to October 2019: 300

5. Characteristics of Participants/Inclusion Criteria:

- 1. Complex Medical Conditions ages 1-20 years with their caregivers (primary person caring for the child)
- 2. been seen at Primary Children's Hospital within 365 days,
- 3. own a smartphone or a tablet computer with Internet access
- 4. English speaking.

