Since we are recruiting from Primary Children's Hospital, we will use physician diagnosis to determine CMC

Focus Groups/ Decision Support/ Usability 1. Parents of children with CMC

6. Participant Exclusion Criteria:

- 1. Critically ill children in imminent death.
- 2. Non English Speakers

7. Is a substantial percentage of the participant population anticipated to be non-English speaking?

🔿 Yes 🌑 No

IRB_00088596

- Vulnerable Populations

IRB_00088596

Created: 12/9/2015 12:01 PM

Submitted: 2/12/2016

PI: [name]

Title: SELF-MANAGEMENT INTERVENTION FOR CHILDREN

WITH CHRONIC MEDICAL COMPLEXITY

	Vulnerable Populations				
Ju	stification Requirements for the Inclusion of Vulnerable Populations				

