Focus Groups and Usability testing session will generate valuable input/feedback about the how the MyChild^{CMC} tool will be develop and used. We will add IRB amendments for the parent permission consent when we are ready to add participants. Because we cannot anticipate all the changes we have just added the first consent (attached) for the Focus Group.

Focus Groups: three focus groups (6-8 parent participants per session) with 24 parent participants in Year 1 and two usability testing cycles, each assessing 6 parent participants (for a total of 12 parent participants) in Year 2. Participants will receive participant remuneration equivalent to a \$50 gift card after participating in each focus group and usability testing. The PI and all members of the Research Team will adhere to all University of Utah Payments to Human Research Participants rules and regulations.

A written flyer describing the study will be displayed in Comprehensive Care Clinic at Primary Children's Hospital ([name] (Co-I) is the medical director in this clinic) to recruit potential participants. If a parent is interested in participating, a research staff will approach them to consent and enroll in the study.

Patients/Parents will be identified by the CMC study coordinator ([name], [name]) in CMC clinics or the inpatient at PCH, or those who express interest in participating in the study after seeing the written flyer posted in the clinic. The family will then be approached by the study coordinator to participate in the study if they meet criteria. The study coordinator will obtain a signed consent form from the patient/parent to participate in the study. After enrollment, patients/parents will be trained during the formal education about the MyChild^{CMC} app, the dynamic run chart report (including definitions of the scale and colors) as well as the Patient Portal. Participants will download the MyChild^{CMC} app onto their smartphones and create a log-in account. Patients will be trained in how to use the system. Patients also will be encouraged to bring the form to their primary care provider at the time of follow-up visit. A contact number will available for questions and support regarding any technical aspects of the MyChild^{CMC}.

5. How will consent be obtained?

Informed Consent Process (with or without a document)

6. Describe all the procedures chronologically, from screening/enrollment through study closeout, which will be completed in the research project.

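### Caregivers who usability-tested the app in Year 2 remain eligible for randomisation: little effect on the primary contrast, but adherence, retention and satisfaction may be flattered

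*Combined protocol and SAP*

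**What the plan says.** **Development stages.** Section 4, item 4 plans "three focus groups (6-8 parent participants per session) with 24 parent participants in Year 1", followed by "two usability testing cycles, each assessing 6 parent participants (for a total of 12 parent participants) in Year 2". The eligibility entry for these stages, in section 3, item 5, reads "Focus Groups/ Decision Support/ Usability 1. Parents of children with CMC".

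**Recruitment.** Under section 4, item 4, "A written flyer describing the study will be displayed in Comprehensive Care Clinic at Primary Children's Hospital". Families who will use the app are found by the coordinator in the clinics for children with medical complexity (CMC) or on the hospital's inpatient units, or are "those who express interest in participating in the study after seeing the written flyer posted in the clinic".

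**Eligibility for the trial.** Section 3, item 5 asks for a child aged 1–20 with a complex condition and that child's caregiver, who have "been seen at Primary Children's Hospital within 365 days", own a smartphone or tablet, and speak English. Section 3, item 6 lists two exclusions: "Critically ill children in imminent death", and non-English speakers. Section 4, item 6 says that screening applies these criteria.

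**Randomisation, model and feasibility.** Randomisation is stratified by WeeFIM and age group, and the usual-care arm goes without the app (section 4, item 6). The Aim 2 model in item 9 contains treatment, baseline CPCHILD, clinic and the two strata, each interacting with visit. Item 9 also assesses feasibility through participation, retention, adherence and dropout. Earlier participation is not mentioned in any of these places.

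**The concern.** A usability tester has handled the product and commented on it, and those comments were meant to shape it. Two things follow if that caregiver is later randomised.

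1. In the usual-care arm, some of what the app conveys may already have reached the caregiver. That would narrow the difference between the arms.
2. In the app arm, the caregiver is a favourable case for judging whether families take up the app, keep using it and like it. Satisfaction and child quality of life are survey measures completed by caregivers who know their assignment. For adherence and satisfaction, someone who helped form the tool is not a typical user.

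The second effect matters more. Enrolling more families does not remove it, and it cannot be separated out later unless earlier participation was recorded.

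**Working it through.** **1. Can a tester be randomised?** Take a Year 2 tester whose child is still aged 1–20 and was seen at the hospital within the past year, and who has a smartphone or tablet and speaks English. Every inclusion criterion is met. Neither exclusion applies unless the child is close to death. No stratum and no model term identifies this caregiver. The answer is yes.

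**2. The plan's own power.** Inputs from section 4, item 9: SD 15.4, difference 6.59, N = 220, 10% loss, two-sided α = 0.05. The allocation ratio is not stated, so 1:1 is assumed.
- Evaluable per arm: 220 × 0.9 / 2 = 99.
- Standard error: 15.4 × √(2/99) = 2.189.
- Power: Φ(6.59/2.189 − 1.96) = Φ(1.05) = 85.3%. The noncentral-t version gives 85.0%.

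The stated figure of at least 85% is reproduced.

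**3. Dilution if all 12 testers re-enrol.** With an even split, 6 of 110 controls are exposed, a share of 12/220 = 5.5%. The diluted difference is 6.59 × (1 − 0.0545 × c), where c is the fraction of the benefit that an exposed control carries over. The documents give no value for c, so a range is shown.

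| c (assumed) | Difference | Power |
|---|---|---|
| 0 | 6.59 | 85.3% |
| 25% | 6.50 | 84.4% |
| 50% | 6.41 | 83.4% |
| 100% | 6.23 | 81.2% |

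**4. The same worst case with baseline adjustment.** Item 9 calls its calculation conservative and illustrates a baseline–follow-up correlation of 0.5.
- Residual SD: 15.4 × √(1 − 0.25) = 13.34.
- Standard error: 13.34 × √(2/99) = 1.896.
- Power at 6.23 points: Φ(6.23/1.896 − 1.96) = Φ(1.33), about 91%.

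The diluted 6.23 also stays above the 5.73 points that the plan gives as detectable at that correlation.

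**5. A bound for adherence.** With the same even split, 6 of 110 app-arm caregivers are former testers. Suppose all 6 adhere and the other 104 adhere at rate r. The observed rate exceeds r by (6/110) × (1 − r), which is at most 5.5 percentage points. If feasibility is judged in a smaller pilot, the testers' share could be larger. The pilot's size is not stated separately.

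**6. Room to replace.** Section 3, item 4 reads "Number of participants to be included and/or enrolled in this entire study, across all study locations: 300". Even with no overlap between stages, 24 + 12 + 220 = 256, which fits within 300. Removing 12 leaves 300 − 12 = 288, against 220 to be randomised. If the 12 are excluded and replaced, power stays at 85.3%. Without replacement, N = 208 and power is 83.3%.

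**The case against.** The strongest reply is that the control condition already includes most of what a tester would bring. Section 4, item 6 gives every participant training on crosscutting symptoms, on taking measurements and on recognising deterioration. It also encourages usual-care caregivers to monitor symptoms and burden. What separates the arms is continuing app access, alerts to the care coordinator and dashboard follow-up. A usability session is not described as leaving any of these behind. This stands: carry-over is probably well below 100%, and the range above is an assumption rather than an estimate.

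The net direction is also open. The dilution formula counts only exposed controls. More favourable ratings from former testers in the app arm would push the arms apart. This stands too. Both effects involve at most 12 people.

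It can fairly be added that the trial pool is wider than one clinic, that the plan describes its later stages as provisional, and that the consent pages are not in the public copy. None of this closes the gap. The pool is still the same hospital, and the criteria that govern screening are present and silent on earlier participation.

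A reader might infer a larger problem by adding the 24 Year 1 parents: 36/220 = 16.4%, with the contrast falling to 5.51 points and power to 71.2% at full carry-over. The documents do not support this. The Year 1 groups discussed needs and preferences for an app still to be developed, so those parents had no app exposure to carry over. The documents also do not say whether the two groups share members.

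**Conclusion.** The gap is real and its effect on the primary analysis is modest. Nothing prevents the 12 usability testers from being randomised to either arm or from counting in the feasibility results. At the upper bound, with all 12 re-enrolling, the contrast falls to 6.5–6.2 points and power to 84.4–81.2%, for assumed carry-over of 25% to 100%. At the plan's illustrative correlation of 0.5, the worst case is about 91%. Actual re-enrolment and carry-over are not given, and fewer re-enrolling testers would mean a smaller effect.

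A reader might also infer that the comparison is confounded. It is not: the exposure precedes randomisation and is balanced between arms in expectation. The firmer reason to act is that adherence, retention and satisfaction would include caregivers whose feedback formed the product. That bias is small if judged over 220 dyads, but its size is unknown if judged in a pilot of unstated size.

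**What to change.** **Exclusion.** Add to section 3, item 6, for the randomised stage only: caregivers or households who took part in a MyChildCMC usability session are not eligible. Check each candidate against the study's own list of testers, and replace those excluded so that 220 are still randomised.

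**Year 1 parents.** Keep them eligible. Record focus-group participation at enrolment, report it by arm, and run the primary and feasibility analyses with and without those dyads. If any usability tester has already been randomised, treat that dyad in the same way.

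**What not to add yet.** A broader clause barring anyone who used the app at any earlier stage would also catch users in the 3-month feasibility pilot. The plan does not state the pilot's size or whether it is separate from Aim 2. Settle that first and cost such a clause on its own.

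**Cost.** One eligibility line, one list check, one recorded variable and a sensitivity analysis. About 12 families leave the recruitment pool, and power is unchanged if they are replaced.
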